9.2 Evaluation After Recurrence

Investigations Evaluations after pelvic and/or extra pelvic recurrence		Timing from the date of first recurrence (see Section10.3)
Physical Exam including:	
 • performance status • weight • tobacco smoking status 	At the time of first recurrence* AND Years One to Three – q 6 monthly Then q 12 months until study closure.
Pelvic Exam	
 • recto-vaginal examination with speculum or colposcopy** 	
Radiology	
 • CT or MRI scan of abdomen and pelvis • chest radiograph 	If clinically indicated
Adverse Events***	
 • Patients must be evaluated for related adverse events at each follow-up visit. 	Years One to Three – q 6 monthly Then q 12 months until study closure.

* A full “work-up” for pelvic recurrence is required at the time extra-pelvic recurrence is diagnosed. ** A recto-vaginal examination is preferred but not mandatory. A bimanual exam is also acceptable. *** Adverse events will be recorded and graded according to the NCI Common Terminology Criteria for Adverse Events (CTCAE) Version 4.0 (Appendix V). Only AEs deemed possibly, probably, or definitely related to protocol therapy need to be reported.
		

10.0 CRITERIA FOR MEASUREMENT OF STUDY ENDPOINTS

As relapse-free survival is an important endpoint in this study, it is vital that it be adequately and precisely documented.

10.1 Definitions

The major parameters of outcome are pelvic recurrence rate at 3 years, pelvic and extra-pelvic relapse-free survival and overall survival.

- 10.1.1 Pelvic recurrence rate at 3 years is defined as a probability of pelvic recurrence within 3 years from randomization. A pelvic recurrence is defined as a recurrence within the pelvis, below the pelvic brim and inferior to the L4-L5 vertebral level. Pelvic recurrences will include disease recurrence in the vaginal vault, parametrium and pelvic lymph nodes (including the common iliac nodes).
- 10.1.2 Pelvic Relapse-Free Survival is defined as the date from randomization to the date of first documented reappearance (recurrence) of disease provided that this recurrence is in the pelvis.
- 10.1.3 Extra-Pelvic Relapse-Free Survival is defined as the date from randomization to the date of first documented reappearance (recurrence) of disease provided that this recurrence is outside of the pelvis. An extra-pelvic recurrence is defined as a recurrence outside of the pelvis, including above the pelvic brim and/or superior to the L4-L5 vertebral level. Extra-pelvic recurrences will include the para-aortic lymph nodes.
- 10.1.4 Recurrence is defined as new clinical, imaging or cellular/tissue-based specimen evidence of cervical cancer since study entry.
- 10.1.5 Site of First Recurrence (i.e. para-aortic or supraclavicular lymph nodes, lung, liver, bone, etc.) will be documented.
- 10.1.6 Overall Survival is defined as the time from randomization until death from any cause. For living patients, the date corresponding to the most recent date of patient contact (regardless of whether this date is protocol required) will be used.

10.2 Evidence of Disease Recurrence

Evidence of disease recurrence may be based on clinical, imaging or cellular/tissue based specimen evidence. Ideally, recurrence is based on a cellular or tissue – based analysis. In specific circumstances, imaging tests may provide compelling evidence of disease recurrence and the subsequent management of the patient is based on these results. Rarely, clinical findings unsupported by a specimen-based analysis or definitive imaging are considered to show sufficient evidence of disease recurrence. For the CX.5 protocol, the following policies for determining evidence of disease recurrence will apply:

- i) Cellular/tissue-based specimen evidence: Histologic evidence is considered the gold standard for disease recurrence. When a histologic sample has not been obtained, but there are definitive cytologic findings of recurrent cervical cancer, the patient will be considered to have recurrent cervical cancer based on the results of a specimen analysis.
- ii) Imaging based evidence: Imaging-based evidence will be considered sufficient for a diagnosis of recurrent cervical cancer if these findings are considered unequivocal OR are subsequently supported by specimen-based evidence.
- iii) Clinical evidence: Clinical-based evidence will be considered sufficient for a diagnosis of recurrent cervical cancer if this evidence is unequivocal (e.g. speculum/colposcopic visualization; a palpable mass) AND is subsequently supported by specimen-based evidence OR unequivocal imaging evidence. When clinical evidence is supported by imaging findings that are considered sufficient to justify recommencing therapy for cervical cancer, the imaging findings will be judged as providing unequivocal evidence of recurrent cervical cancer.

10.3 Dating of First Recurrence

This should always be based on the onset of a sign but never on the onset of a symptom. The date of first detection of a palpable and/or visible lesion is acceptable only when these findings are unequivocal and a diagnosis of tumour involvement is subsequently established by pathological or radiologic confirmation. The diagnosis of recurrent disease by radiographs or scans alone should be dated from the date of the first unequivocally positive record, even if this is determined in retrospect. Initial recording of dates of first recurrence and death should be made as they occur by those who are responsible for the care of the patient. Dates that are based on suspicion alone without unequivocal evidence will be reviewed by the CCTG trial team to establish their accuracy through subsequent behaviour. In addition, the case records of those patients not reported as having recurrent disease will be scrutinized regularly to check that review is continuing and to ensure consistent recording.

10.4 Management Following Recurrence

Patient management following recurrence is at the discretion of the investigator. Protocol follow-up should continue until trial completion.

11.0 SERIOUS ADVERSE EVENT REPORTING

The descriptions and grading scales found in the NCI Common Terminology Criteria for Adverse Events (CTCAE) will be utilized for Adverse Event (AE) reporting (version can be found in Appendix V). All appropriate treatment areas should have access to a copy of the CTCAE. A copy of the CTCAE can be downloaded from the CTEP web site:

(http://ctep.cancer.gov/protocolDevelopment/electronic_applications/ctc.htm).

All serious adverse events (SAE) defined as per ICH guidelines (see below) and other adverse events must be recorded on case report forms. In addition, all “reportable” serious adverse events are subject to expedited reporting using the CCTG SAE form. The term ‘reportable SAE’ is used in the definitions which follow to describe those SAEs which are subject to expedited reporting to CCTG.

11.1 Definition of a Reportable Serious Adverse Event

- All serious adverse events which are unexpected and related to protocol treatment (as defined in Section 8) must be reported in an expedited manner (see Section 11.2 for reporting instructions). These include events occurring during protocol treatment and at any time afterwards.
- Unexpected adverse events are those which are not consistent in either nature or severity with known complications.
- Adverse events considered related to protocol treatment are those for which a relationship to the protocol treatment cannot reasonably be ruled out.
- A serious adverse event (SAE) is any adverse event that:
 - results in death
 - is life-threatening
 - requires inpatient hospitalization or prolongation of existing hospitalization (excluding hospital admissions for study drug administration, transfusional support, scheduled elective surgery and admissions for palliative or terminal care)
 - results in persistent or significant disability or incapacity
 - is a congenital anomaly/birth defect

Medical and scientific judgement should be exercised in deciding whether expedited reporting is appropriate in other situations such as important medical events that may not be immediately life-threatening or result in death or hospitalization but may jeopardize the patient or may require intervention to prevent one of the events listed above.

11.2 Serious Adverse Event Reporting Instructions

All reportable serious adverse events must be reported using a web-based Electronic Data Capture (EDC) system being used for this trial. For details about accessing the EDC system and completing the on-line SAE report form, please refer to the CCTG Generic Data Management Guidebook for EDC Studies posted on the CX.5 section of the CCTG website (www.ctg.queensu.ca).

Within 24 hours: Complete preliminary Serious Adverse Event Report and submit to CCTG via EDC system.

Within 10 days: Update Serious Adverse Event Report as much as possible and submit report to CCTG via EDC system.

EDC SAE web application interruption:

In the rare event that internet connectivity to the EDC SAE system is disrupted, please print and complete a paper copy of the SAE Report, available from the trial specific website.

FAX paper SAE Report to:

CX5 Study Coordinator
Canadian Cancer Trials Group
[contact]

Note: Centres outside of Canada are asked to please refer to their group-specific appendix for additional, detailed instructions regarding SAE reporting.

Please use the same timelines for submission as for direct EDC reporting.

Once internet connectivity is restored, the information that was FAXED to CCTG on the paper SAE Report must also be entered by the site into the EDC SAE web application.

Local internet interruption:

If you are unable to access the EDC SAE system, and cannot access a paper copy of the SAE Report from the trial website, please phone the CX.5 trial team [contact]) to obtain a copy of the SAE Report by FAX. Once completed, the report must be FAXED back to CCTG as indicated above. Once internet connectivity is restored, the information that was FAXED to CCTG on the paper SAE Report must also be entered by the site into the EDC SAE web application.

In cases of prolonged internet interruptions, please contact the CCTG Safety Desk for further instructions [contact]).

11.3 Reporting Safety Reports to Investigators

CCTG will notify Investigators of all Safety Reports (Serious Adverse Events (SAEs) from this trial and relevant information from other clinical trials) that are reportable to regulatory authorities in Canada as reported to the CCTG. This includes all serious events that are unexpected and related (i.e. possibly, probably, or definitely) to protocol treatment. The reports will be posted to the CCTG trial CX.5 web-based safety monitoring utility.

Investigators must notify their Research Ethics Boards (REBs) of events which involve corrective action(s) to be taken as a result of the event(s) such as protocol and/or informed consent changes. The date of REB Submission for these SAEs will need to be entered into the CCTG trial CX.5 web-based safety monitoring utility and documentation of REB submission must be retained in the study binder on site. The REB submission template provided by CCTG can be used to assist with tracking, submission, filing and monitoring.

The submission of events to your ethics board should be done as soon as possible (we suggest within 30 days). REB submissions greater than 90 days from the date of notification will be regarded as delinquent and a major deficiency will be assigned. These safety reports are to be filed in the trial files on site.

12.0 PROTOCOL TREATMENT DISCONTINUATION AND THERAPY AFTER STOPPING

Patients may not receive protocol treatment (as defined in Section 8) in the following instances:

- Intercurrent illness which would, in the judgement of the investigator, affect assessments of clinical status to a significant degree.
- Request by the patient.

Efforts should be made to maintain the investigations schedule and continue follow-up, even if patients do not undergo surgery and/or no longer attend the participating institution.

12.1 Therapy After Protocol Treatment

The management of patients who complete protocol treatment (or who never undergo protocol treatment) is left to the discretion of the Investigator. The visit schedule for those patients who receive other anti-cancer therapy should not be modified as endpoints will be assessed for as long as the patient can be followed and an intent-to-treat analysis will be performed.

12.2 Follow-Up After Protocol Treatment

Follow-up will continue after treatment completion to monitor patients for study endpoints. Participants should be followed by in-person clinic visits to the greatest extent possible. Follow-up assessment by telephone or other remote method is allowed, if permitted by local policy, only in emergency situations (refer to Appendix VIII) or for participants who have permanently ceased follow-up at the recruiting centre but are not lost to follow up. In the latter circumstance, the recruiting centre will remain responsible for procuring and reporting follow-up data per protocol schedule. The recruiting centre should document the reason why in-person follow-up visits are unable to continue at their centre and how relevant study data will be obtained for future follow up periods.

12.3 Lost to Follow Up

Participants will only be declared lost to follow up (LTFU) if there has been a minimum of 3 unsuccessful contact attempts documented over 2 or more years after the last date of successful contact. Required methods of contact include contacting the participant by telephone and searching relevant medical records, if permitted by local site policy. All participant contact attempts must be clearly documented in the patient's medical record.

13.0 CENTRAL REVIEW PROCEDURES AND TISSUE COLLECTION

13.1 Central Review of Diagnostic Imaging and Quality Assurance Procedure

There will be no up-front central radiology review for this study. De-identified MRI scans may be collected by CCTG and reviewed by the CX.5 Radiology Coordinator should the need arise. It is recommended that each site designate a Local Reference Radiologist (LRR) who will be responsible for reviewing the pre-study MRIs for all CX.5 patients; however, this is not mandatory. The description of the MRI specifications outlined in section 5.1.5 was designed to facilitate and standardize the diagnostic imaging for this trial.

13.2 Pathology Quality Assurance

Each CCTG participating centre will identify one Local Reference Pathologist (LRP) who is the designated gynecologic pathologist (on the Participants List). *For non CCTG centres, this process will be described in your cooperative group procedures document.*

The LRP will be responsible for reviewing:

1. The diagnostic pathology specimen for all study patients to confirm their eligibility for the trial. The LEEP/Cone/Biopsy Checklist that is part of the Surgery/Pathology Manual was designed to facilitate and standardize this review.
2. The post-surgical hysterectomy and lymphadenectomy/sentinel node specimens. The Hysterectomy Checklist that is part of the Surgery/Pathology Manual was designed to facilitate and standardize this review.
3. The specimen that diagnoses disease recurrence.

Note: CCTG may require that any or all of the abovementioned specimens be submitted for central pathology review (see section 13.4)

13.3 Surgical Quality Assurance Procedure

13.3.1 Hysterectomy

A photograph of the “unpinned” hysterectomy (modified radical or simple) specimen will be submitted as part of the supporting documentation required for the Surgery Report. The CX.5 Study Chair will review these pictures along with other supporting documentation as part of the surgical quality assurance process. Please see the Surgery/Pathology manual for submission details.

[figure not shown]
13.3.2 Sentinel Node Mapping Procedure

It is understood that patients will undergo surgery performed by a trained gynecologic oncologist. Prior to local activation, the site must declare:

1. Whether or not they will be employing sentinel node mapping for their CX.5 patients.
2. Whether each gynecologic oncology surgeon listed on the Participants List has treated at least 10 cervical and/or endometrial cancer patients using the SN mapping technique per the standards outlined in the protocol and this manual.

Then, the first 5 cases for each qualified surgeon performing sentinel node mapping as part of the CX.5 trial must undergo a quality assurance exercise. This exercise will consist of the following steps:

Centre completes all required case report forms (baseline report and surgery form) and
--

Note: it is recommended that this exercise is completed as soon as possible following each surgery so that important feedback may be communicated back to the surgeon before another patient undergoes protocol treatment. It is not expected that this exercise will delay a potential randomization or a patient's surgery; unless under exceptional circumstances.

13.4 Central Pathology Review

There will be no up-front central pathology review for this study; however, tissue samples from procedures that show disease recurrence may be collected for central review by the CX.5 trial Pathology Coordinator should the need arise.

14.0 STATISTICAL CONSIDERATIONS

14.1 Objectives and Design

The primary objective of this study is to compare the pelvic recurrence rate at 3 years of patients with low-risk cervical cancer defined as lesions less than 2 cm, at least 3mm of intact cervical stroma or with less than 50% stromal invasion and randomized to receive simple hysterectomy and pelvic node dissection or radical hysterectomy and pelvic node dissection. Secondary objectives include comparisons of pelvic relapse-free survival, overall survival, extra pelvic relapse-free survival, rate of sentinel node detection, rate of parametrial, margins and pelvic nodes involvement, treatment-related adverse events, and quality of life (including sexual health). Eligible patients will be randomized in a 1:1 ratio to one of the two treatment arms using the minimization method and the following stratification factors: cooperative group, intended use of SN mapping (yes vs. no); stage (IA2 vs. IB1), histological type (squamous vs. adenocarcinoma, adenosquamous) and tumour grade (1-2 vs. 3 vs. not assessable).

14.2 Primary Endpoints and Analysis

Pelvic recurrence rate at 3 years, the primary endpoint of this study, will be estimated by the Kaplan-Meier estimate for the 1-probability of pelvic relapse-free survival (PRFS) at 3 years, where the PRFS is defined as the time from randomization to the time when any documented evidence of recurrence within the pelvic field (see Sections 10.0-10.3). Patients who relapsed outside of the pelvic field or died before the documentation of pelvic relapse will be censored at the time of first documented extra pelvic relapse or death. If the patient is alive without any relapse at the time of final analysis, PRFS will be censored on the date of the last disease assessment. All patients will be included in the analyses in the arms to which they are randomized regardless of whether they receive the assigned treatment (intention-to-treat). Upper limit of a one-sided 95% confidence interval for the difference in the pelvic recurrence rates at 3 years between simple hysterectomy to radical hysterectomy will be calculated based on the Greenwood estimate for the variance of the estimated 3 year PRFS and non-inferiority of simple hysterectomy to radical hysterectomy will be claimed when this upper limit is lower than or equal to 4%. A “per-protocol” sensitivity analysis based on only eligible patients who have received any study treatment and analyzed based on arms they are treated will also be performed for non-inferiority testing.

The experience of PRFS, a secondary endpoint of the study, will be described by the Kaplan-Meier method for all randomized patients in both treatment groups on the base of intention-to-treat. Based on Jung *et al.* (sample size computation for two-sample non-inferiority log-rank test, [Jung, 2005]), non-inferiority of simple hysterectomy to radical hysterectomy will be claimed when the upper limit of a one-sided 95% confidence interval for the hazard ratio of simple hysterectomy to radical hysterectomy, derived from a stratified Cox model adjusting for stratification factors at randomization and with a single treatment covariate, is lower than or equal to 2.04. The non-inferiority margin 2.04 for hazard ratio is corresponding to a margin of 4% for the 3 year PRFS between simple hysterectomy and radical hysterectomy when the 3-year PRFS in radical hysterectomy was estimated at 96%. A “per-protocol” sensitivity analysis will also be performed.

Other secondary efficacy endpoints include (1) overall survival, defined as time from randomization to the time of death from any cause. Patients who are alive at the time of the final analysis or who have become lost to follow-up will be censored at their last contact date; and (2) extra pelvic relapse-free survival free survival, defined as time from randomization to the time of first documented relapse outside the pelvic field. Patients who had pelvic relapse or died before extra pelvic relapse will be censored at time of pelvic relapse or death. Patients who are alive without any recurrent disease at the time of the final analysis will be censored at their last disease

assessment dates. Analyses for these secondary efficacy endpoints will be done using similar methodology for PRFS. For the rest of the secondary endpoints, the rate of sentinel node detection and rate of parametrial, margins and pelvic nodes involvement, they will be compared between two arms using a Fisher's exact test.

All patients who have received study treatment will be included in the adverse events analysis based on arms they are treated. Adverse events will be graded using the NCI Common Toxicity Criteria Version 4.0. The incidence of adverse events will be summarized by type of adverse event and severity. A Fisher's exact test will be used as needed to compare adverse events between the two arms.

14.3 Sample Size and Duration of Study

It is estimated that the pelvic recurrence rate at 3 years for the radical hysterectomy is around 4% and we would consider simple hysterectomy is non-inferior to radical hysterectomy if its pelvic recurrence rate at 3 years is 8% or less. With 350 patient randomized to each of the two treatment arms, the study will have around 85% power to conclude the non-inferiority at 0.05 level when the pelvic recurrence rate at 3 years is the same in the two arms. Final analysis will be performed when the last patient randomized has been followed for 3 years.

14.4 Safety Monitoring

Adverse events will be monitored on an ongoing basis by Central Office. Their frequencies will be reported annually at investigators' meetings. In addition adverse events will be reviewed by the DSMC every 6 months and also by the Safety Conference Committee according to CCTG policy. As well, the annual report will include number of cases in each arm with positive nodes (abandoned protocol treatment).

14.5 Interim Analysis

No interim analysis will be performed.

14.6 Analysis for Quality of Life

The quality of life and sexual health of patients in this study will be assessed by respectively EORTC QLQ-C30 core questionnaire with its module QLQ-CX24, the Female Sexual Function Index (FSFI), and the Female Sexual Distress Scale (FSDS-R). The EORTC QLQ-C30 and QLQ-CX24 are self-administered cancer specific questionnaires with multi-dimensional scales. QLQ-C30 consists of both multi-item scales and single item measures, including five functional domains, a global quality of life domain, three symptom domains, and six single items, while QLQ-CX24 has three multi-item subscales: symptom experience, body Image, and sexual/vaginal functioning, and five single items pertaining to menopausal symptoms, lymphedema, lower back pain, tingling and numbness, and sexual enjoyment. FSFI is a 19-item self-report measure of female sexual function that provides scores on six domains of sexual function (desire, arousal, lubrication, orgasm, satisfaction, and pain) as well as a total score. The FSDS-R is a 13-item unidimensional measure of sexually-related distress. Scoring of the quality of life and sexual health data will be completed following the procedures recommended by the EORTC Study Group on Quality of Life and other published algorithms.

The quality of life and sexual health data will be analyzed to look for statistically and clinically significant differences between two treatment arms. Questionnaire compliance rates will first be ascertained for each group at each measurement time point. Mean scores at baseline and the change scores from baseline at each follow-up assessment time point will be calculated for each subscale and summary scores and compared between two arms by Wilcoxon test. The profile of change scores over time between two treatment arms will be compared using linear mixed models.

The basic hypotheses in QOL and sexual health data analysis are, on average, women managed with simple hysterectomy had lower change scores from baseline on QLQ-CX24 symptom subscale and FSDS-R total score and higher change scores from baseline on FSFI total score relative to women in the radical hysterectomy group. Based on estimates of pooled standard deviations of 13.5, 10 and 21 respectively for change scores on QLQ-CX24 symptom subscale and FSDS-R and FSDS-R total score, we need respectively a total of 120, 130 and 560 women with QOL and sexual health assessments to detect respectively 7, 5, 5 points difference between two treatment arms with 80% power and two-sided 0.05 level in these subscale and scores.

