Sexual distress is what motivates individuals to seek treatment for sexual difficulties. Given this, and given the finding that changes in genital sensations/arousal are considered to be the primary source of symptom-associated distress following surgical treatment of cervical cancer, sexual distress will be considered our primary outcome and overall sexual functioning as a secondary outcome within the sexual health analyses [Bergmark 2002].

The FSFI [Rosen 2000] is a validated measure of sexual desire, orgasm, lubrication, pain, and satisfaction widely available in a variety of languages. It is a 19-item self-report measure of female sexual function that provides scores on six domains of sexual function as well as a total score. Domains include: Desire (2 items), Arousal (4 items), Lubrication (4 items), Orgasm (3 items), Satisfaction (3 items), and Pain (3 items). Items are scored on a 5-point Likert scale with higher scores corresponding with better sexual functioning. The FSFI has been shown to reliably discriminate women with Female Sexual Arousal Disorder from sexually-healthy controls on each of the six domains of sexual function as well as the Full Scale score [Rosen 2000]. The FSFI was found to be internally consistent (Cronbach's alpha ranged between 0.82 and 0.98;) and test-retest reliabilities using a 4-week interval ranged between $r = 0.79$ and 0.86 [Rosen 2000].

The FSDS-R [Derogatis 2002, Dergogatis, 2008] is a 13-item measure of sexually-related distress available in English and French. Items are scored on a 5-point Likert scale. Scores range from 0 – 48, where higher scores represent higher levels of sexual distress. The FSDS-R has been shown to have good discriminant validity for differentiating between sexually dysfunctional and sexually functional women [Derogatis 2002, Dergogatis, 2008]. There is also satisfactory consistency, test-retest reliability, and moderate correlations with measures of nonsexual distress.

Table 1: Quality Of Life Instruments (in addition to the Global Quality of Life instrument EORTC QLQ-C30)

Instrument	Estimated mean baseline	Estimated change with simple hyst.	Estimated change with radical hyst.	Difference we wish to test for (delta) i.e. the differential between arms	Estimated pooled std deviation of the scores
EORTC CX.24 symptom subscale	3	+3 (mean score 6)	+10 (mean score 13)	7	13.5
FSDS-R total score	22*	+5	+10	5	10
FSFI Total Score	33.3*	-5	-10** (mean score 23)	5	21

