7.8.1.3 FSFI

The FSFI is a 19-item self-report measure of female sexual function that provides scores on six domains of sexual function (desire, arousal, lubrication, orgasm, satisfaction and pain) as well as a total score:

- Desire $(Q1+Q2) * 0.6$
- Arousal $(Q3+...+Q6) * 0.3$
- Lubrication $(Q7+...+Q10) * 0.3$
- Orgasm $(Q11+...+Q13) * 0.4$
- Satisfaction $(Q14+...+Q16) * 0.4$
- Pain $(Q17+...+Q19) * 0.4$
- Total Score $(Q1+...+Q19) / 19 * 1.2$

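### The FSFI planning inputs and the FSFI scoring are mutually inconsistent, so the stated requirement of 560 women is not supported

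*Protocol*

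**What the plan says.** Protocol Section 14.6 bases the patient-reported sample sizes on "pooled standard deviations of 13.5, 10 and 21 respectively for change scores on QLQ-CX24 symptom subscale", and the sentence continues "and FSDS-R and FSDS-R total score, we need respectively" totals of 120, 130 and 560 women. The aim is "to detect respectively 7, 5, 5 points difference between two treatment arms", "with 80% power and two-sided 0.05 level in these subscale and scores". The FSDS-R is named twice and the FSFI not at all. Table 1 in Section 2.5.4 shows that the third entry is the FSFI total.

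Table 1 gives the FSFI total a baseline mean of 33.3, planned changes of −5 (simple) and −10 (radical), a difference of 5 and an SD of 21. Its column for the SD is headed "Estimated pooled std deviation of the scores", whereas Section 14.6 treats the same 21 as an SD of change. The table cites a source for the baseline mean and for the radical-arm change, but none for the SD.

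SAP Section 7.8.1.3 gives weights for six FSFI domains, for example "Arousal $(Q3+...+Q6) * 0.3", and then a total: "Total Score $(Q1+...+Q19) / 19 * 1.2". Neither document states the range of the FSFI total.

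**The concern.** A sample size for a mean difference is only as good as its SD, and the SD must be possible on the scale that will be analysed. Here the SD looks too large for any FSFI total that the documents define. The FSFI is also the outlier of the three instruments: 7/13.5 = 0.52 and 5/10 = 0.50 for the other two, but 5/21 = 0.24 for the FSFI.

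FSFI total score is the subject of one of the three key quality-of-life hypotheses in Protocol Section 2.5.3. Section 14.6 is the only place that gives it a sample size, since SAP Section 5 covers pelvic recurrence alone. The stated number is 560/700 = 80% of all planned patients, for a questionnaire that Protocol Section 6.0 makes optional. A reader who judges the precision of the FSFI result against 560 would be using a figure that the documents do not support.

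**Working it through.** **1. Reproduce 560.** Inputs from Section 14.6: difference 5, SD 21, 80% power, two-sided 0.05, with 1:1 allocation from Section 14.1.

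Per arm: n = 2 × [(1.960 + 0.8416) × 21/5]² = 2 × 11.767² = 276.9, so 277 per arm and 554 in total. The t-test version gives 556. The companion figures fit the same method: 118 to 120 for the QLQ-CX24 (120 stated) and 126 to 128 for the FSDS-R (130 stated). The formula is sound, so the question is the input of 21.

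**2. Range of the FSFI total.** The top item score is 5 (Protocol Section 2.5.4). With the SAP weights the domain maxima are 2 × 5 × 0.6 = 6 (desire), 4 × 5 × 0.3 = 6 (arousal, lubrication) and 3 × 5 × 0.4 = 6 (orgasm, satisfaction, pain). Six domains sum to at most 36. The printed SAP total gives at most 95/19 × 1.2 = 6.

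**3. Table 1's label: SD of scores.** On 0 to 36 no distribution has an SD above 36/2 = 18. At a given mean m the limit is √[(36 − m) × m]: 9.5 at 33.3, 14.8 at 28.3 and 17.2 at 23.3. A higher floor lowers these limits. An SD of 21 is impossible.

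**4. Section 14.6's label: SD of change.** The range alone allows up to 36, so Table 1's means are needed. For baseline mean a and follow-up mean b on 0 to 36, the largest variance of change is 36 × [(36 − a) + (36 − b)] − (b − a)².

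- Simple: 36 × (2.7 + 7.7) − 5² = 374.4 − 25 = 349.4, so SD ≤ 18.7.
- Radical: 36 × (2.7 + 12.7) − 10² = 554.4 − 100 = 454.4, so SD ≤ 21.3.
- Pooled with equal arms: √[(349.4 + 454.4)/2] = √401.9 = 20.05.

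The limit is reached only if every woman scores 0 or 36 at each visit and no woman scores 0 at both. A floor of 2 lowers the pooled limit to 19.4, and a floor of 7.2 (every item scored 1) lowers it to 17.6. A pooled 21 is excluded.

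**5. The SAP total as printed.** With a maximum of 6, a baseline of 33.3 and an SD of 21 cannot occur, and a planned difference of 5 would be nearly the whole scale.

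**6. What other SDs would need.** The documents give no replacement SD, so these SDs are assumptions. N uses the formula in step 1, rounded up per arm. Power with 560 women is Φ[5/(SD × √(2/280)) − 1.96].

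| Assumed SD | Total N | Power with 560 |
|---|---|---|
| 10 | 126 | above 99.9% |
| 14 | 248 (246 before rounding) | 98.8% |
| 17 | 364 | 93.6% |
| 18 (limit for scores) | 408 | 90.8% |
| 20.05 (limit for pooled change) | 506 (505 before rounding) | 83.9% |
| 21 (as stated) | 554 | 80.4% |

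**The case against.** The 36-point maximum is derived, not stated. Protocol Section 14.6 refers scoring partly to published algorithms that are not reproduced, and the weights come from an SAP section whose total formula is itself doubtful. On an unweighted sum of 19 items (maximum 95) an SD of 21 is attainable. Table 1 may also mix two scorings: 33.3 out of 36 would be near-perfect function, yet the title of its cited source concerns women with sexual dysfunction. This stands to the extent that the documents do not show whether the SD, the means or the scale is at fault. It does not rescue 560, because neither document defines an unweighted sum as the FSFI total. If that sum was used for planning, the power statement refers to a scale that the SAP does not analyse.

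A reader might infer that the FSFI scale by itself rules out an SD of 21. For change scores it does not, and the exclusion needs Table 1's means as well. A reader might also infer that the comparison is underpowered or out of reach. The documents do not support that: on the 36-point scale the error makes 560 too large, and no section uses 560 as a threshold.

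The practical weight is modest. Enrolment was set by pelvic recurrence, accrual closed in November 2019, the Wilcoxon and mixed-model analyses do not use the planning SD, and Protocol Section 2.5.4 ranks sexual function behind sexual distress. All of this stands.

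**Conclusion.** The concern holds as an inconsistency among the SD, the planned means and the scoring. The 560 depends on an SD of 21. On the sum of the SAP's six weighted domains that value exceeds the limit of 18 for scores and the limit of about 20.0 for pooled change. On the SAP's printed total none of the planning values makes sense.

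The conclusion rests on three assumptions: the intended total is the sum of the six domains, Table 1's means are on that scale, and the floor is 0, which is the most generous choice.

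The size of the error cannot be fixed from the documents. Assumed SDs from 10 up to the ceiling of about 20 give roughly 126 to 505 women. A reader might take one of the lower figures as the correct requirement, but no FSFI SD in the documents supports choosing it. The error understates power. It does not weaken the FSFI comparison or touch the primary endpoint.

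**What to change.** - In SAP Section 7.8.1.3, define the FSFI total as the sum of the six domain scores and state its range. The printed formula gives every item the weight 1.2/19 = 0.063, so it is not merely a rescaled domain sum.
- In Protocol Section 14.6, name the third scale as the FSFI total instead of repeating the FSDS-R.
- In Table 1 and Section 14.6, say whether the SD is of scores or of change, put it on the same scale as the means and the difference, and give its source.
- Restate the number of women. If no sourced SD is available, show a range by assumed SD, as in the table above, and label the SDs as assumptions.

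The cost is a few text corrections, one restated figure and one scoring formula. Data collection, enrolment and trial conduct do not change.
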